5.2.11. Prohibited Study Medication

Medications defined as prohibited for use during the study according to Appendix B, "Guidance on Potential Interactions with Concomitant Medications" will be documented during screening. Patients must stop taking any prohibited medications and have completed the required "washout" period prior to starting AZD4547, as per exclusion criterion 12.

5.2.12. Physical Examination

A complete physical examination will be performed, as per local practice at the scheduled visits indicated in the Study Plan. The following examinations should be undertaken: general appearance, skin, head and neck, lymph nodes, thyroid, musculoskeletal/extremities, cardiovascular, respiratory, abdomen and neurological. The outcome of the examinations will be assessed as normal or abnormal, and whether clinically significant.

5.2.13. ECOG Performance Status

Performance status will be assessed at the scheduled visits indicated in the Study Plan according to ECOG criteria as follows:

- 0 = Fully active, able to carry on all predisease activities without restriction
- 1 = Restricted in physically strenuous activity but ambulatory and able to carry out work of a light or sedentary nature. For example, light housework, office work
- 2 = Ambulatory and capable of all self care but unable to carry out any work activities. Up and about more than 50% of waking hours
- 3 = Capable of only limited self-care, confined to bed or chair 50% or more of waking hours
- 4 = Completely disabled. Cannot carry on any selfcare. Totally confined to bed or chair
- 5 = Death

5.2.14. Vital Signs

Vital signs including weight, pulse and blood pressure will be measured at the scheduled visits indicated in the Study Plan. Vital signs may be assessed at any time during the visit; however, supine blood pressure and pulse should be measured after 10 minutes rest. Height will be measured at initial screening visit only.

5.2.15. ECG

A standard 12-lead ECG will be performed as indicated in the Study Plan. The patient should be examined with the same machine throughout the study.

ECGs will be recorded at the following time points:

- Screening
- Cycle 1 day 8: 2 hours post morning dose of study medication (AZD4547 + either anastrozole or letrozole)
- Cycle 2 day 1 (and each subsequent cycle): any time on the day of assessment

- At discontinuation of AZD4547 + either anastrozole or letrozole therapy

Details of rhythm, ECG intervals and an overall evaluation will be collected.

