5. STUDY PLAN AND PROCEDURES

5.1. Study Schedules

Scheduled visits are uniquely identified by study period, and day within the period. The combination treatment period of the safety run-in study and the phase IIa study are further partitioned into consecutively numbered treatment cycles of 28 days duration. The period and day when scheduled visits occur, as well as, observations and assessments required during the study are summarised in Table 1 for the safety run-in and Table 2 for phase IIa.

In the phase IIa study, unless indicated otherwise, scheduled assessments may take place within ± 1 day of the scheduled day, e.g, laboratory evaluations scheduled for cycle 1 day 7 may take place on cycle 1 day 6 or day 8. Assessment days will all be relative to the start of study treatment, i.e. Cycle 1 Day 1.

If a patient has AZD4547 treatment breaks, please contact the Study Team for advice regarding appropriate timing of PD biomarker assessments. All other assessments, including laboratory safety assessments, vital signs and RECIST should continue to be performed as described in the appropriate sections of the protocol, relative to the baseline assessments

Table 1: Study Plan (Safety run-in)

Study Period	Screening	NSAI ¹ monotherapy		AZD4547 + NSAI ¹ combination								AZD4547 / NSAI ¹ Discont.	28-day follow-up
		n/a		Cycle 1				Cycle 2		Cycle 3	Cycle 4 (onwards)		
Activity / Day	-28 to -1	1	7	1	7	15	21	1	15	1	1		
Inclusion/exclusion criteria & informed consent	X												
Demographics	X												
Medical history / Concomitant medical conditions	X	X	X	X	X	X	X	X		X	X	X	
Radiotherapy (previous/current) ²	X	X	X	X	X	X	X	X		X	X	X	X
Chemotherapy (previous/current)	X												X
Surgical History	X												
Disease Extent/Tumour Characteristics	X												
Concomitant medication	X	X	X	X	X	X	X	X		X	X	X	X
Prohibited medication	X												
Physical examination	X	X	X					X		X	X	X	
ECOG performance status	X	X	X		X	X	X	X		X	X	X	X
Vital signs	X		X					X		X	X	X	X
ECG	X				X			X		X	X	X	
Echo / MUGA scan	X							X ³				X	
Laboratory evaluations (blood/urine)	X		X		X	X	X	X		X	X	X	X

Study Period	Screening	NSAI ¹ monotherapy		AZD4547 + NSAI ¹ combination								AZD4547 / NSAI ¹ Discont.	28-day follow-up
		Cycle	n/a	Cycle 1				Cycle 2	Cycle 3	Cycle 4 (onwards)			
Activity / Day	-28 to -1	1	7	1	7	15	21	1	15	1	1		
Ophthalmic assessment	X							X		X	X ⁴	X	
Treatment compliance			X	X	X	X	X	X		X	X	X	
PI disease status assessments	X								X		X		

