Pharmacokinetic sampling			X		X								
Blood sample PD biomarkers	X		X		X	X	X					X	
Treatment dosing		Treatment will be administered according to details in Section 6.2.3.											
DLT assessment				X	X	X	X	X					
Adverse events		X	X	X	X	X	X	X		X	X	X	X
Archival tumour (optional)	X												
Paired tumour biopsy (optional)	X							X ⁵					
Pharmacogenetic sample (optional)		X											

¹ Either anastrozole or letrozole

² **ONLY** radiation for palliation at focal sites is permitted whilst the patient is on study medication

³ After the cycle 2, day 1 assessment, MUGA/ECHO should be performed every three months i.e. at the end of cycles 4, 7 etc. and at discontinuation of AZD4547.

⁴ After first 3 months of AZD4547, ophthalmological review should be every 8 weeks (+/- 1 week) until permanent discontinuation of AZD4547

⁵ The second biopsy should be collected during cycle 2, but as close to completion of 1st cycle of study treatment as possible

Notes: Activities in italic are unique to Safety run-in study.

Table 2: Study Plan (Phase IIa)

Study period	Screening	AZD4547 + NSA1 ¹ combination									AZD4547 / NSA1 ¹ Discont.	28-day follow-up
		Cycle	n/a	Cycle 1				Cycle 2		Cycle 3		
Activity / Day	-28 to -1	1	8	15	22	1	15	1	1	1		
Inclusion/exclusion criteria & informed consent	X											
Archival tumour ² sample (mandatory) / exploratory (optional)	X											
Demographics	X											
Medical history / Concomitant medical conditions	X	X	X	X	X	X	X	X	X	X	X	
Radiotherapy (previous/current) ³	X	X	X	X	X	X	X	X	X	X	X	X
Chemotherapy (previous/current)	X											X
Endocrine Therapy (previous)	X											
Targeted Therapy (previous)	X											
Surgical History	X											
Disease Extent/Tumour Characteristics	X											
Concomitant medication	X	X	X	X	X	X	X	X	X	X	X	X
Prohibited medication	X											
Physical examination	X	X		X		X		X	X	X	X	
ECOG performance status	X	X	X	X	X	X	X	X	X	X	X	X
Vital signs	X	X		X		X		X	X	X	X	X
ECG	X		X			X		X	X	X	X	
Echo / MUGA scan	X							X ⁴			X	

Study period	Screening	AZD4547 + NSA1 ¹ combination									AZD4547 / NSA1 ¹ Discont.	28-day follow-up
Cycle	n/a	Cycle 1				Cycle 2		Cycle 3	Cycle 4	Cycle 5 (onwards)		
Activity / Day	-28 to -1	1	8	15	22	1	15	1	1	1		
Laboratory evaluations (blood/urine)	X	X	X	X	X	X	X	X	X	X	X	X
Ophthalmic assessment	X					X		X	X ⁵		X	
Treatment compliance			X	X	X	X		X	X	X	X	
Tumour assessments as per RECIST 1.1	X						X		X ⁶		X	
Blood sample PD biomarkers ⁷	X		X	X	X	X		X	X	X	X	

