6.2.3. Dosage and Duration

AZD4547 will be administered orally twice daily in a tablet formulation. A cycle of treatment will be defined as 28 days: one week of AZD4547 twice daily in combination with either anastrozole or letrozole once daily, followed by one week of either anastrozole or letrozole once daily alone, and the intermittent schedule repeated once more to complete one cycle.

For procedures relating to dose modification, dosing interruption and restarting of AZD4547 for subjects in both the safety run-in and phase IIa study, see 6.2.8.

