6.2.3.2. Phase IIa

The dose of AZD4547 to be used in combination with anastrozole and letrozole in the phase IIa part of the study has been determined in the safety run-in, i.e. 80 mg, twice daily given on an intermittent schedule of one week on/one week off.

N.B. If 2 or more cases of severe toxicity (leading to permanent discontinuation of study drug) are observed in the first 6 patients, an alternative schedule of two weeks on / one week off will be considered, if emerging data from other AZD4547 studies suggest that this is a better tolerated schedule. A cycle of treatment will be defined as 28 days: e.g. Cycle 1, two weeks of AZD4547 twice daily in combination with either anastrozole or letrozole once daily, followed by one week of either anastrozole or letrozole once daily alone, then one week of AZD4547 twice daily in combination with either anastrozole or letrozole once daily to complete the cycle.

6.2.4. Definition of Dose-Limiting Toxicity for assessment of safety and tolerability of AZD4547 in the safety run-in study

A DLT is defined as any toxicity not attributable to the disease or disease-related processes under investigation, which occurs after the first dose of AZD4547 at start of cycle 1 and before the end of cycle 1 (the DLT assessment window) and includes:

1. Haematological toxicity = CTCAE grade 4 present for more than 4 days
2. Non-haematological toxicity \geq CTCAE grade 3 including:
 - Infection including febrile neutropenia (Grade 3 with temperature $\geq 38.5^{\circ}\text{C}$ or Grade 4 with temperature $\geq 38^{\circ}\text{C}$)
 - QTc prolongation (> 500 msec) or QTc increase > 60 msec from baseline

3. Any other toxicity that is greater than that at baseline, is clinically significant and/or unacceptable, does not respond to supportive care and results in a disruption of dosing schedule of more than 14 days
4. Any event, including significant dose reductions or omissions, judged to be a DLT by the SRC

A DLT excludes:

1. Alopecia of any grade
2. Isolated laboratory changes of any grade without clinical sequelae or clinical significance

6.2.5. Definition of Severe Toxicity for Assessment of Safety and Tolerability of AZD4547 in the PIIa study

For the purposes of the PIIa study, severe toxicity is defined as indicated above (6.2.4), but occurring after the first dose of AZD4547 at start of cycle 1 until study treatment discontinuation.

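### The only dose-timed Phase IIa ECG is set on Cycle 1 day 8, the first day without AZD4547 under the schedule in use; it should be day 7

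*Protocol*

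**What the plan says.** Section 5.2.15 lists four kinds of ECG: at screening; at "Cycle 1 day 8: 2 hours post morning dose of study medication (AZD4547 + either anastrozole or letrozole"); on day 1 of Cycle 2 and each later cycle, at any time that day; and at discontinuation. Table 2 ("Table 2: Study Plan (Phase IIa")) marks the Cycle 1 ECG under day 8, without dose timing.

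The dosing text is in section 6. Section 6.2.3 defines a 28-day cycle as a week of AZD4547 with the aromatase inhibitor, "followed by one week of either anastrozole or letrozole once daily alone", with that pair of weeks then repeated. Section 6.2.3.2 gives the Phase IIa dose as "determined in the safety run-in, i.e. 80 mg, twice daily given on an intermittent schedule of one week on/one week off". A fallback, to be considered only after two or more severe toxicities in the first 6 patients, would open Cycle 1 with "two weeks of AZD4547 twice daily in combination with either anastrozole or letrozole once daily".

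Section 5.1 fixes the day count ("Assessment days will all be relative to the start of study treatment, i.e. Cycle 1 Day 1") and the Phase IIa window ("scheduled assessments may take place within ± 1 day of the scheduled day"). Its example of that window reads "laboratory evaluations scheduled for cycle 1 day 7 may take place on cycle 1 day 6 or day 8".

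**The concern.** The ECG is tied to a dose that the schedule does not give on that day. A site following the printed day has three choices: take the ECG with no AZD4547 dose that morning, use the window to move to day 7, or give an AZD4547 dose on an off day.

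This ECG is the only one in Phase IIa meant to be read at a fixed time after a dose, following repeated dosing. QTc above 500 msec, or a rise of more than 60 msec, counts as severe toxicity (6.2.4, applied to Phase IIa by 6.2.5). Severe toxicity leading to permanent discontinuation feeds the first-6-patients rule in section 3.2. If sites resolve the conflict differently, the Cycle 1 ECGs of the 50 patients will fall at mixed times after the last dose, and section 5.2.15 does not list clock time among the ECG data collected (the eCRF may hold it).

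**Working it through.** No power or sample-size figure is involved. The check is a day count.

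**Inputs.** Day 1 is the start of study treatment (5.1). Schedule in use: 7 days on, 7 days off (6.2.3, 6.2.3.2). Fallback: 14 days on, 7 days off (6.2.3.2). Window: ±1 day (5.1).

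**Dosing days in Cycle 1.** With *a* days on and *b* days off, day *d* is a dosing day if (*d* − 1) mod (*a* + *b*) < *a*.

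| Schedule | AZD4547 days | Day 7 | Day 8 | Day 9 |
|---|---|---|---|---|
| 7 on / 7 off (in use) | 1–7, 15–21 | 6 mod 14 = 6 < 7: on | 7 mod 14 = 7: off | 8 mod 14 = 8: off |
| 14 on / 7 off (fallback) | 1–14, 22–28 | 6 < 14: on | 7 < 14: on | 8 < 14: on |

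The instruction can be met on 1 of the 3 window days under the schedule in use, and on 3 of 3 under the fallback.

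**Time since the last AZD4547 dose.** The protocol says only that dosing is twice daily, so clock times are assumed: morning dose 08:00, ECG at 10:00, evening dose 18:00, 20:00 or 22:00. On days 8 and 9 the last dose is the evening dose of day 7.

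| ECG day | Evening 18:00 | Evening 20:00 | Evening 22:00 |
|---|---|---|---|
| 7 | 2 h | 2 h | 2 h |
| 8 | 6 + 10 = 16 h | 4 + 10 = 14 h | 2 + 10 = 12 h |
| 9 | 16 + 24 = 40 h | 14 + 24 = 38 h | 12 + 24 = 36 h |

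If the morning dose time varies from 07:00 to 09:00 (ECG 09:00 to 11:00), the ranges become 2 h on day 7, 11–17 h on day 8 and 35–41 h on day 9.

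**Can another ECG supply the reading?** Table 2 schedules post-baseline ECGs to Cycle 5 on study days 8, 29, 57, 85 and 113 (1 + 28*k* for *k* = 1 to 4 after the first), plus discontinuation: 6 in all. Days 29, 57, 85 and 113 each restart AZD4547 after 7 days off and may be done at any time; discontinuation has no dose timing. So 1 of the 6 is dose-timed, and its printed day is an off day.

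**Which day fits the rest of the protocol?** Run-in Table 1, on the same regimen, marks the Cycle 1 ECG on day 7. Section 5.2.15 carries no run-in or Phase IIa tag, so its day 8 also disagrees with Table 1. The run-in PK profile, which includes a 2-hour sample, is on day 7 of Cycle 1 (5.3.1). The Phase IIa window example in 5.1 names a Cycle 1 day 7 laboratory visit that Table 2 does not contain.

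**Literal compliance.** With two doses on day 1, a patient has taken 7 × 2 = 14 AZD4547 doses by the end of day 7. A day 8 morning dose given to satisfy 5.2.15 would be a 15th, on an off day.

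**The case against.** The strongest reply is that the protocol already contains the remedy. The dose condition and the ±1-day window, read together, leave only day 7, and a careful site would find it; a day 9 ECG would ignore the explicit dose condition. That stands as mitigation. It does not correct the printed day, which both 5.2.15 and Table 2 give as day 8, and it asks the window to rescue an instruction that cannot be met on its nominal day.

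A second reply is that day 8 could be right if the first AZD4547 dose is taken late on day 1, for instance while blood results are awaited under 5.2.17. Fourteen doses would then end on the morning of day 8. This may happen in individual patients, but the protocol states it nowhere, and timing that relied on it would vary by patient. It does qualify the dose count above and any claim that day 8 can work only under the fallback.

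The supporting evidence for day 7 is also indirect. Table 1 and the PK profile belong to the run-in, and the 5.1 example concerns laboratory tests. They indicate the likely intention; the contradiction itself rests on 5.2.15 and 6.2.3.

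Finally, the consequence is small. Section 1.6.4 presents regular ECGs as a way to detect functional change from possible mineralisation and describes no QTc signal. The run-in scheduled a day 7 ECG on this regimen, and a day 8 ECG still follows a full week of dosing by about one dosing interval. The link to the first-6-patients rule is remote, since QTc is one criterion among several and the event must lead to permanent discontinuation. All of this stands and limits the severity.

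**Conclusion.** The concern holds. Counted from Cycle 1 Day 1 with a full day of dosing on day 1, day 8 has no AZD4547 dose under the schedule in use, so the ECG instruction cannot be met on its printed day. What is lost is the 2-hour post-dose reading after a week of dosing, not all on-drug information. The 11–17 h and 35–41 h intervals for days 8 and 9 rest on assumed clock times; the day count does not. No effect on QTc has been estimated, and the efficacy endpoint is not affected. This is an operative safety instruction that should be corrected, with limited consequence if it is not.

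**What to change.** In section 5.2.15 and the ECG row of Table 2, set this ECG on Cycle 1 day 7 with a window of −1/0 day, 2 hours after the morning AZD4547 dose. Table 2 needs a day 7 column or a footnote for it. Record the ECG clock time, so that the interval from the dose time already kept in the patient diary (5.2.19) can be calculated. Day 7 is a dosing day under both the schedule in use and the fallback, so one wording serves both and also agrees with Table 1.

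If the day 8 attendance must be kept, state a maximum interval from the previous AZD4547 dose, as 5.5.1.3 does for the day 22 biopsy, and accept that the 2-hour reading is given up.

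The cost is a text and table amendment with the same number of ECGs. A day 7 ECG may need an attendance separate from the day 8 visit. If the whole visit moves to day 7, section 5.2.17 requires that day's blood results before the first AZD4547 dose, so the dose and the ECG would fall later in the day.

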5.2.16. Echocardiogram and/or MUGA Scan

An echocardiogram and / or MUGA scan to assess left ventricular ejection fraction (LVEF) will be performed at screening, Cycle 3 day 1 (± 1 week), then every 3 months (± 1 week) and finally at AZD4547 discontinuation visit.

5.2.17. Laboratory Evaluations

Blood and urine samples for haematology, clinical chemistry and urinalysis will be taken at scheduled visits and analysed at the local laboratory using standard methods for routine tests. NB. **On dosing days for all cycles, samples must be taken pre-dose**; as on these visit days, samples must be processed, and results available, prior to administration of the first daily dose of AZD4547 to ensure an assessment of patient suitability to resume dosing is undertaken.

The following variables will be measured:

Clinical Chemistry: ALT, AST, Alkaline phosphatase, Bilirubin (total), Corrected Calcium (total), Creatinine (total), Random glucose, Magnesium, Phosphate, Potassium, Sodium, Troponin I or Troponin T, Urea nitrogen, Albumin

Haematology: Haemoglobin, Leukocyte, Neutrophils, Lymphocytes, Platelets

Urinalysis: Glucose, Protein, Blood

Urinalysis parameters will be measured using a dipstick test. If there are any abnormalities found the urine sample will be sent for Micro Culture Sensitivity Testing

N.B. Management of patients will be according to the corrected calcium result and corrected calcium:phosphate product. Where corrected calcium is not provided by the site laboratory the following formula should be used:

Corrected Calcium = Total Calcium (mmol/L) + $([40 - \text{Albumin (G/L)}] \times 0.02)$

The corrected calcium phosphate product (Ca:PO₄) is calculated by multiplying the corrected calcium result by phosphate result:

Ca:PO₄ = Phosphate (mmol/L) $\times ((\text{Total Calcium (mmol/L)} + ([40 - \text{Albumin (G/L)}] \times 0.02))$

Laboratory values that have changed significantly from baseline and are considered to be of clinical concern must be recorded as an adverse event and followed up as appropriate.

5.2.18. Ophthalmic Assessment

An ophthalmic assessment will be performed by an ophthalmic expert at screening, Cycle 2 day 1, Cycle 3 day 1 and Cycle 4 day 1 (± 3 days), as shown in the study plan (Table 1 and Table 2). Thereafter, patients continuing the study treatment should have a full ophthalmological review every 8 weeks (± 1 week) and finally at AZD4547 discontinuation visit. At any other time, abnormal visual symptoms or signs will trigger a full ophthalmological review. Algorithms for further management are provided in Figure 5 and Figure 6 in Section 6.2.8 "Dose Modifications for AZD4547".

The ophthalmic assessment should be performed on each occasion by the same ophthalmic expert where possible.

The following assessments will be performed in the order stated:

- (i) Visual acuity (best corrected) including near and distance vision for each eye separately
- (ii) Amsler grid
- (iii) Schirmer's test without anaesthesia – read after 5 minutes (this test should be done before instillation of stains or dilatory agents)
- (iv) Slit lamp examination:
 - Apply 1 drop of 2% fluorescein followed by 1 drop of normal saline
 - Measure intra-ocular pressure
 - Photograph any abnormalities
- (v) Fundoscopy and lens examination following pupil dilatation should be performed using binocular equipment and a 78 dioptre lens (or nearest available equivalent lens)
- (vi) OCT scans of the macula area of both eyes should be performed at screening and monthly for the first 3 months on study treatment. After this time, an OCT scan should be performed on the occurrence of clinical symptoms or signs suggestive of RPED. OCT is the preferred methodology for diagnosis of RPED. If OCT is not available as part of local clinical practice, an equivalent alternative diagnostic methodology to screen for RPED should be used.

Clinically significant abnormalities detected during ophthalmic assessments should be reported as AEs. The patient should be managed under the care of a competent ophthalmologist with appropriate medication and followed up until the condition has resolved.

A central review of ophthalmology reports may be undertaken throughout the study.

5.2.19. Treatment Compliance (Patient Diary)

Patients will keep a detailed record of all study medication that they take in their patient diaries. Date and time of administration, drug name and drug dose will be collected.

5.2.20. Principle Investigator Disease Status Assessments (Safety Run-In only)

Principle Investigator (PI) disease status assessments will be performed using CT, MRI or plain x-ray to assess any progression of the patient's disease. The clinician must document: date of assessment, imaging method used (X-ray, CT or MRI), site (breast, lung, liver, pleural effusion, local lymph nodes, distant lymph nodes, bone, brain or other) and outcome of assessment. Disease status assessments will be performed at screening, Cycle 2 day 15 and Cycle 4 day 1.

5.2.21. Tumour Assessments (Phase IIa only)

Tumour assessments will be performed using CT or MRI scans of the chest, abdomen and pelvis. The same method used for assessment at baseline must be used at all subsequent time points.

Tumour assessment will include: if disease is measurable or non-measurable (at least one lesion must be measurable), date of assessment, imaging method used, site (breast, lung, liver, pleural effusion, local lymph nodes, distant lymph nodes, bone, brain or other site), longest diameter of each target lesion and sum of longest diameters for all target lesions.

Patient response to treatment will be assessed using RECIST v1.1 criteria. Tumour size, Progression Free Survival and Objective Response Rate will all be determined.

Tumour Size, will be assessed at baseline and on scans at subsequent time points and recorded as the sum of the longest diameters of the target lesions.

Progression Free Survival (PFS) is defined by the progression criteria of RECIST.

Objective Response Rate (ORR) is defined as the percentage of patients who have at least one visit response of CR or PR prior to any evidence of progression (as defined by RECIST v1.1)

The RECIST v1.1 (January 2009) guidelines for measurable, non-measurable, target and non-target lesions and the objective tumour response criteria (complete response, partial response, stable disease or progression of disease) are detailed in Appendix A

Baseline assessment should be performed no more than 28 days before the start of study treatment and ideally as close as possible to the start of study treatment; it should include all areas known for possible breast cancer metastases.

Subsequent tumour assessments will be conducted at week 6, week 12 (primary endpoint) and then every 8 weeks until objective disease progression or cessation of study treatment and finally at AZD4547 discontinuation visit. The window for each assessment is ± 1 week.

Duplicates will be made of all CT/MRI scans. These duplicate scans will be collected to enable an independent review of progression.

